### **Incomplete Stop Date**

#### **Missing day and month**

- If the year of the incomplete stop date is the same as the year of the last visit date, then the day and month of the last visit date will be assigned to the missing fields.
- If the year of the incomplete stop date is before the year of the last visit date, then December 31 will be assigned to the missing fields.
- If the year of the incomplete stop date is after the year of the last visit date, then January 1 will be assigned to the missing fields.

#### **Missing month only**

- The day will be treated as missing and both month and day will be replaced according to the above procedure.

#### **Missing day only**

- If the month and year of the incomplete stop date are the same as the month and year of the last visit date, then the day of the last visit date will be assigned to the missing day.
- If either the year is before the year of the date of the last visit date or if both years are the same but the month is before the month of the last visit date, then the last day of the month will be assigned to the missing day.
- If either the year is after the year of the date of the last visit date or if both years are the same but the month is after the month of the date of the last visit date, then the first day of the month will be assigned to the missing day.

In case that the start date is after the stop date after missing value calculation, the non-computed date will replace the computed date. If both are computed, replace the stop date with the start date.

### **APPENDIX 3: ANALYSIS WINDOW**

For the analyses described in Section 13.1, visits are defined as follows:

- If a subject was not able to provide blood or urine collection at a scheduled visit and has the assessments performed at a later unscheduled visit, the unscheduled assessments will be mapped to the previous scheduled visit.
- If there are multiple unscheduled assessments, the one closest to the scheduled visit will be mapped.

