### **5.5.1 Permitted Concomitant Therapies**

The Investigator may prescribe concomitant medications or treatments deemed necessary to the subject without any impact on study participation, with the exception of those medications defined in Section 5.5.2 of this protocol.

Subjects who start any non-buprenorphine MAT or transmucosal buprenorphine treatment will not be discontinued from the study. Information on MAT initiation, dosing regimen, potential changes in dose and cessation of therapy must be documented.

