f Urine pregnancy tests will be performed for any woman of childbearing potential (defined as all women who were not surgically sterile or postmenopausal for at least 1 year prior to informed consent). Pregnancy is not exclusionary for enrolment and pregnancy during the study does not lead to discontinuation.

g Only adverse events related to study procedures and/or study conduct should be collected in the eCRF.

h Concomitant medications are all medications taken during the study, including any prescribed medication-assisted treatment (methadone, naltrexone, buprenorphine) and will be captured. Of note, any extended-release buprenorphine treatment initiation will lead to study discontinuation.

i Ask about the subject's illicit buprenorphine use in the last 14 days. If the subject has used prescribed and not illicit buprenorphine, capture in Concomitant Medications. Illicit use will not impact the subject's participation on the study.

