#### 13.1 DESCRIPTIVE ANALYSIS

The number and percentage of subjects with negative and positive results for buprenorphine on the qualitative UDS will be summarized for FAS Part A at Visit 1 and for FAS Part B across Visits 1, 2 and 3. Qualitative UDS results for opioids other than buprenorphine will be summarized in a similar way.

The number and percentage of subjects with negative results for **both** buprenorphine and norbuprenorphine based on quantitative UDS or free drug concentrations will be summarized for FAS Part A at Visit 1 and for FAS Part B across Visits 1, 2 and 3. Negative and positive results for each analyte will also be summarized (buprenorphine, norbuprenorphine and naloxone for quantitative UDS; buprenorphine and norbuprenorphine for free drug concentrations). A negative result will be any concentration below the lower limit of quantification (LLOQ). A positive result will be any quantifiable concentration.

As for urine, the number and percentage of subjects with negative results for **both** buprenorphine and norbuprenorphine concentrations in plasma will be summarized for FAS Part A at Visit 1 and for FAS Part B across Visits 1, 2 and 3. Negative and positive results for each analyte (buprenorphine, norbuprenorphine) will also be summarized. A negative result will be any concentration below the LLOQ. A positive result will be any quantifiable concentration.

For all above tables, missing data will not be imputed. For Visits 2 and 3, data associated with the reported use of illicit buprenorphine at the visit or the use of prescribed buprenorphine within 3 weeks of the assessment will be excluded from all the above summary statistics calculation for that visit only. Those excluded data, if any, will be indicated in the listings. With respect to Visit 1, no data should be excluded since meeting the exclusion criteria infers that there was no use of prescribed or illicit opioid use within 3 weeks prior to the Screening visit.

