### 13.2.2 Dataset Preparation

Buprenorphine plasma concentration data collected in Parts A and B will be merged with the previous NONMEM dataset that was used to develop the population model presented in Section 13.2.1.

R software version 3.4.3 or older will be used for data inspection and for the preparation of the input datafile for the population PK analysis in NONMEM. This will involve obtaining the required study variables from the primary data source for the current and previous studies, calculating the elapsed time from the last SUBLOCADE dose in Study RB-US-13-0003 or Study INDV-6000-301, and merging with the previous dataset combining Phase II/III data. All R codes related to data preparation, identification of potential outliers, and exploratory graphical analysis will be adequately commented for ease of use.

The NONMEM input file will be formatted as a comma separated (.csv) file and will include the following information: subject unique identification number, dosing information, actual sampling times, measured buprenorphine plasma concentrations, demographics (e.g., sex, age, weight, body mass index [BMI], race), study identification number, and flags for potential outliers and concentrations below the LLOQ.

Plasma concentrations below the LLOQ in the current study will be included in the analysis and will be handled using appropriate likelihood-based methodology.

Plasma concentrations associated with the reported use of illicit buprenorphine at the visit or the use of prescribed buprenorphine within 3 weeks of the visit (Part B – Visits 2 and 3) will be flagged as outliers, and although listed in the NONMEM dataset, will not be used for the population PK analysis.

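### A Visit 1 make-up sample can be drawn after new buprenorphine use and still be counted as residual SUBLOCADE, because the Visit 1 no-exclusion rule covers use only up to Screening

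*SAP*

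**What the plan says.** **Mapping of late samples.** SAP Appendix 3 opens with "For the analyses described in Section 13.1, visits are defined as follows". If a collection was not possible at a scheduled visit and the subject "has the assessments performed at a later unscheduled visit, the unscheduled assessments will be mapped to the previous scheduled visit". It adds: "If there are multiple unscheduled assessments, the one closest to the scheduled visit will be mapped". That chooses between several late samples but does not cap the delay. Late samples are expected: the analysis-set definitions (SAP 6.1.2 and 6.1.3) and the completer definitions (SAP 7) count scheduled and unscheduled collections alike.

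**Visit 1.** SAP 13.1 says: "With respect to Visit 1, no data should be excluded since meeting the exclusion criteria infers that there was no use" of buprenorphine before Screening. The criterion behind this is Protocol 5.3, exclusion 2, which looks back 3 weeks from the Screening visit.

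**Visits 2 and 3.** For the summary tables, SAP 13.1 removes data linked to illicit use reported at the visit, and for prescribed drug says that data associated with "the use of prescribed buprenorphine within 3 weeks of the assessment will be excluded". The concentration-time plots in the same section give such samples a different symbol, with the 3 weeks measured from the visit. For the population PK dataset (SAP 13.2.2), plasma values linked to illicit use reported at the visit are flagged; for prescribed drug the wording is: "the use of prescribed buprenorphine within 3 weeks of the visit (Part B – Visits 2 and 3) will be flagged as outliers". The ratio subgroups in SAP 13.1 are split by intake, yes or no, with no time window.

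**What is permitted and what is asked.** Protocol 5.5.1: "Subjects who start any non-buprenorphine MAT or transmucosal buprenorphine treatment will not be discontinued from the study". Protocol Appendix 1, footnote i: "Ask about the subject's illicit buprenorphine use in the last 14 days". The schedule places that question at Visits 2 and 3 and does not mention unscheduled draws.

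**The concern.** The study asks how long buprenorphine from the depot stays measurable. A positive sample supports an answer only if recent use of another buprenorphine product can be ruled out. On the Screening day, the eligibility criterion is meant to do that. For a Visit 1 sample drawn later, nothing does. The subject may have started a permitted transmucosal product or used illicit buprenorphine since Screening, no illicit-use question is scheduled for Visit 1, and the SAP bars any exclusion.

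Such a sample would be pooled with Screening-day samples in the Visit 1 tables. The error can only add positives, so it runs toward longer apparent persistence.

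The two anchors for prescribed use raise a second problem. The same make-up sample could be dropped from a Visit 2 or 3 table under one wording and kept as an ordinary value in the plot or the PK fit under the other.

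**Working it through.** **1. Each use rule set against a make-up draw L days after the scheduled visit**

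| Analysis | Rule and anchor | Use between visit and draw |
|---|---|---|
| Visit 1 tables (SAP 13.1) | Nothing excluded; eligibility looks back from Screening | Counted, as written |
| Visits 2/3 tables, prescribed | 3 weeks, anchored on the assessment | Excluded |
| Visits 2/3 tables, illicit | Use reported at the visit | Unclear: depends on whether the unscheduled visit counts as the visit and whether the question is repeated |
| Plots, prescribed (SAP 13.1) | 3 weeks, anchored on the visit; symbol only | Unclear |
| Population PK flag (SAP 13.2.2) | Anchored on the visit; Visits 2 and 3 only | Unclear at Visits 2/3; no flag for Visit 1 |
| Population PK outliers (SAP 13.2.3) | Documented use before the visit; discretionary | May be removed if documented |

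Only the first row gives a definite wrong count. The share of the 21 days before a Visit 1 make-up that eligibility covers is max(0, 21 - L)/21: 86%, 67%, 52% and 33% for L = 3, 7, 10 and 14.

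**2. Could recent use matter beside the residual signal?**

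Inputs are the SAP Table 1 typical values: k24 0.0276, k36 0.00362, k64 0.000510 per h; CL 52.0 and Q 79.5 L/h; V4 433 and V5 1110 L; F2 0.0679; k14 1.17 per h with film factor 0.650; F1 0.185 with film factor 1.47. The film factors are read as multipliers. Assumed: 28-day injection interval, a month of 30.4375 days, no covariate effects, no variability.

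The model is the linear system of SAP 13.2.1. Each injection puts F2 x dose in the fast depot and (1 - F2) x dose in the slow depot. The slow depot empties at k36 into the transit compartment and from there at k64 into the central compartment. Disposition uses CL/V4, Q/V4 and Q/V5. Concentration = central amount / V4.

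Check against the plan's own figure: ln 2 / 0.000510 = 1,359 h = 56.6 days, inside the 43 to 60 days of Protocol 1.2.

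Depot-derived plasma buprenorphine after the last injection:

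| Regimen | 12 months | 18 months | 24 months |
|---|---|---|---|
| 6 x 300 mg | 0.111 ng/mL | 0.012 | 0.0013 |
| 2 x 300 then 4 x 100 mg | 0.048 | 0.005 | 0.0005 |

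One 8 mg film (assumed dose): amount absorbed = 8 x 0.185 x 1.47 = 2.18 mg.

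| Time from film to draw | Plasma | Ratio to 0.111 (month 12) | Ratio to 0.012 (month 18) |
|---|---|---|---|
| 1 day | 0.42 ng/mL | 3.8 | 35 |
| 3 days | 0.128 | 1.2 | 11 |
| 7 days | 0.012 | 0.11 | 1 |
| 10 days | 0.002 | 0.02 | 0.2 |

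The ratios are to the 6 x 300 mg values. For a single tablet dose of 2 to 16 mg the range is 0.07 to 0.43 ng/mL at 1 day, 0.022 to 0.13 at 3 days and 0.002 to 0.013 at 7 days. Use within a few days of the draw can therefore match or exceed the typical residual value; use 10 days earlier is small beside it at 12 and 18 months.

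**3. Effect on a reported percentage**

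One subject wrongly turned from negative to positive: 1/60 = 1.7 points in Part A, 1/30 = 3.3 points in a full Part B. The plasma LLOQ and the number of make-up samples are not stated, so the expected bias cannot be computed.

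**The case against.** The strongest reply is that most of the plan already copes.

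- A reader might infer that every use rule ignores the draw date. The documents do not support that: the Visits 2/3 table rule for prescribed drug is anchored on the assessment, and Appendix 3 itself calls the make-up samples assessments. This stands.
- A reader might infer that illicit use before a Visit 2 or 3 make-up is bound to be missed. It is not shown. Appendix 3 calls the make-up an unscheduled visit, and Protocol 8.2 has the question answered at each Part B visit, so it may well be asked again. The schedule is silent, so this is an ambiguity.
- A reader might infer that the mapping distorts the population PK model or the primary plot. Appendix 3 governs only SAP 13.1. The PK dataset uses actual sampling times, and documented use may be removed under SAP 13.2.3. The plot's axis is time since the last injection, so a visit label does not move the point. The plot's rule for prescribed use is not limited to Visits 2 and 3, and a 3-week window around the visit could be read to include days after it. What remains is that removal from the model is discretionary and neither safeguard catches use that nobody asked about.
- Contamination leaves traces. Naloxone is measured in each urine sample, and the norbuprenorphine/buprenorphine AUC ratio is 0.2 to 0.4 for SUBLOCADE against 1.3 to 3.2 for transmucosal product (Protocol 1.2). These help interpretation, but the SAP does not use them to exclude Visit 1 data.
- Missed visits are to be rescheduled as soon as possible (Protocol 6.4.3). That is a soft limit on delay, not a cap.

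None of this answers the Visit 1 tables, where the SAP states its reason for excluding nothing and that reason fails for a late draw.

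**Conclusion.** The point holds for Visit 1 as a definite gap, and for the wording of the use rules as an inconsistency. Buprenorphine taken between Screening and a Visit 1 make-up draw would be counted as residual SUBLOCADE in the Visit 1 tables. The anchors for prescribed use conflict between the tables, the plots and the PK flag. Whether illicit use is asked about again at a Visit 2 or 3 make-up is not stated.

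The size per sample can be material, but not always. A tempting summary is that a contaminated sample is 35 to 220 times the expected value. That is a worst case at month 18: the lower end needs an 8 mg film one day before the draw, and the upper end needs ongoing 16 mg/day (16 x 0.185 x 1.47 x 0.765 mg per 24 h / 52.0 L/h = 2.67 ng/mL; 2.67/0.012 = about 220). At 7 days the 8 mg film only equals the month-18 value. Nor does every make-up sample shift a percentage by 1.7 points: it must be contaminated and otherwise negative.

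The concentrations rest on typical values, the assumed 28-day interval and the assumed doses, and they concern plasma only. With make-up numbers and the LLOQ unknown, the total bias cannot be stated; only its direction is clear. It is worth correcting because the correction is cheap, not because a large error has been shown.

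**What to change.** 1. In SAP 13.1, limit the statement that no Visit 1 data are excluded to samples drawn on the Screening day.
2. For any later sample, at any visit, apply the use rules relative to the actual collection date in SAP 13.1 (tables, plots and ratio subgroups) and in SAP 13.2.2. Prescribed use: within 3 weeks before the sample. Illicit use: as reported on the existing 14-day question. A 3-week window for illicit use would go beyond what that question can support.
3. Replace the assessment and visit anchors with one anchor, the sample, throughout 13.1 and 13.2.2, and extend the population PK flag to Visit 1 samples drawn after the Screening day.
4. In the schedule of events, repeat the buprenorphine question and the concomitant-medication check at every unscheduled sample collection.

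The question asked at the draw then covers the whole interval since the scheduled visit for make-ups up to 14 days late. Beyond that, L - 14 days stay unasked for illicit use, and the listings should show the delay.

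Cost: a few lines of SAP text and one repeated question and medication check at a draw that takes place anyway. Protocol 8.2.2 already requires the date and time of each blood sample; the urine collection date must be available in the same way. No added visits or samples. The downside is that a few make-up samples may be flagged or excluded.

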#### APPENDIX 4: CORRECTION OF URINE CONCENTRATIONS OR URINE-TO-PLASMA CONCENTRATION RATIOS BY CREATININE CONCENTRATION IN URINE

Buprenorphine or norbuprenorphine urine concentration ( $C_{urine}$ ) corrected by creatinine concentration in urine ( $C_{creat}$ ) will be calculated as follows:

$$C_{urine,corr}(\mu g/g \text{ creatinine}) = \frac{C_{urine} (ng/mL)}{C_{creat}(mg/dL)} \times 100$$

Buprenorphine or norbuprenorphine urine-to-plasma concentration ratio corrected by creatinine concentration in urine will be calculated as follows:

$$Ratio_{corr}(\text{per } mg/dL \text{ creatinine}) = \frac{C_{urine} (ng/mL)}{C_{plasma}(ng/mL)} \times \frac{1}{C_{creat}(mg/dL)}$$

Of note:

$$C_{plasma}(ng/mL) = C_{plasma}(pg/mL)/1000$$

$$C_{urine}(ng/mL) = C_{urine}(pg/mL)/1000$$
